7.0 Measurement of Effect

7.1.1 Methods for Pathologic Evaluation

Standard pathologic evaluation will be performed following surgical resection. This evaluation includes measurement of lymph node involvement as well as assessment of histopathologic changes such as necrosis within the tumor. This will be classified as present or absent for the purposes of statistical comparison.

7.1.2 Assessment for efficacy

Germinal center formation has been observed in 35% of lung cancers with the majority of these occurring at the tumor margin. In the clinical

laboratory and the laboratory of [name], IHC will be performed to assess the microenvironment components using an IHC panel. GCs will be assessed as being present or absent and the density GCs at within lymph nodes will be estimated using standard digital microscopy and automated methods under the supervision of [name] and [name]. If necessary, manual assessment of GC density within lymph nodes will be performed and graded as high, moderate, low, or absent.

Adverse Events List and Reporting Requirements

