11.0 Statistical Considerations

11.1 Power and Sample Size

Roughly 35% of lung cancers express germinal centers (GC) with the majority of GCs being detected at the tumor margin. Given our target sample size of n=90 patients per arm, we will have 80% power, using a one-tailed alpha of 0.05, to detect an increase to 53% expressing GCs in the treatment arm, given the expected “background” 35% in the standard-of-care arm. Given the current surgical volume, it is estimated that we will enroll 90 patients per year, so that total accrual will last approximately 2 years.

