11.2 Method of Randomization

Patients will be randomized in a 1:1 ratio to receive the vitamin A treatment intervention or standard of care. Patients will be stratified for randomization based on pre-operative stage (stage 1, 2, or 3).

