Appendix F – Outcomes Data Collection Form

Instructions: Use this form to collect data related to necrosis and number of germinal centers.

Study Number: _____ PID: _____

Investigator: W. [name]. Date: _____ / _____ / _____

1. Necrosis: Present Not Present
2. Germinal centers in tumor: Present Not Present
 - a. Location:
 - i. Intratumoral _____ (Y/N)
 - ii. At margins _____ (Y/N)
3. Density of germinal centers in lymph nodes:
 High Moderate Low Not Present

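### The plan does not state that the tumor germinal-center call, or the manual node grade, is made without knowledge of treatment arm

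*Combined protocol and SAP*

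**What the plan says.** **Design.** Section 11.2 states: "Patients will be randomized in a 1:1 ratio to receive the vitamin A treatment intervention or standard of care". No placebo or sham is described. The product section (9.2) and the medication log (Appendix L) concern vitamin A only.

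**Primary outcome.** Section 5.1.1 makes it binary. Section 7.1.2 says "GCs will be assessed as being present or absent", and Appendix F records it as "Germinal centers in tumor: Present Not Present", with yes/no items for intratumoral and marginal location.

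**Secondary pathology outcomes.** Node GC density is to be estimated by digital microscopy and automated methods. If needed, "manual assessment of GC density within lymph nodes will be performed and graded as high, moderate, low, or absent". Under Section 7.1.1, necrosis comes from the routine pathology work-up after surgery and is classed as present or absent.

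**What is not stated.** The available text does not mention masking of readers, coded slides, reading order, a second reading, or a threshold for calling GCs present. Appendix F has no arm field, and no field showing that a reading was masked.

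**Analysis.** Section 11.1 says "Given our target sample size of n=90 patients per arm" and "we will have 80% power, using a one-tailed alpha of 0.05". Section 11.3.1 plans contingency tables and then logistic regression on arm, stage and age. It does not say whether the test is one- or two-sided.

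**The concern.** Without a placebo, treatment assignment is not concealed by the design, so any protection of the endpoint has to come at the reading step. The plan states no protection there. Section 1.0 also gives the expected direction: retinoids increased GC formation in animal models. With no stated positivity threshold, a doubtful tumor is left to judgment. If the person judging knows the arm, doubtful cases may be resolved differently in the two arms.

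That would be differential misclassification arising after randomization. Balanced allocation does not prevent it, and adjustment for stage and age does not remove it. At stake is whether a positive primary result can be attributed to vitamin A rather than to the reading.

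**Working it through.** **Inputs from Section 11.1.** 90 per arm; control GC rate 35%; target rate 53%; one-sided alpha 0.05; stated power 80%.

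**Assumption, not in the documents.** No true effect (35% in both arms), but the recorded rate in the vitamin A arm alone is raised by *d* points. Values of 3, 5 and 10 points are shown.

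**Step 1: reproduce the plan's power.** Power = Φ{[Δ√n − z·√(2p̄(1−p̄))] / √(p₁(1−p₁)+p₂(1−p₂))}, with Δ = 0.18, n = 90, p̄ = 0.44 and z = 1.645.

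- Numerator: 0.18 × 9.487 − 1.645 × √0.4928 = 1.708 − 1.155 = 0.553.
- Denominator: √(0.2275 + 0.2491) = 0.690.
- Power = Φ(0.80) = 78.8%.

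Exact enumeration of the one-sided pooled z test gives 79.4%. The stated 80% is reproduced, so the power figure is not in question.

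**Step 2: false-positive rate under a one-arm reading shift.** Sum Bin(x; 90, 0.35) × Bin(y; 90, 0.35 + d) over all pairs (x, y) that reject. The z test rejects when Z = [(y − x)/90] / √(p̄(1−p̄)·2/90) exceeds the critical value, with p̄ = (x + y)/180. Because Section 11.3.1 leaves the sidedness open, three tests are shown.

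| Shift *d* | Tumors of 90 (90 × *d*) | Share of truly GC-negative tumors (*d*/0.65) | One-sided 0.05 z | One-sided 0.05 Fisher | Upper tail, two-sided 0.05 z |
|---|---|---|---|---|---|
| 0 | 0 | 0% | 5.1% | 3.6% | 2.6% |
| 3 points | 2.7 | 4.6% | 11.3% | 8.6% | 6.4% |
| 5 points | 4.5 | 7.7% | 17.7% | 14.0% | 10.6% |
| 10 points | 9 | 15.4% | 40.7% | 34.9% | 28.3% |

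Hand check at 5 points, using the Step 1 formula:

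- Numerator: 0.05 × 9.487 − 1.645 × √0.46875 = 0.474 − 1.126 = −0.652.
- Denominator: √(0.2275 + 0.2400) = 0.684.
- Φ(−0.95) = 17.0%, against 17.7% exact.

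**Step 3: the same point in counts.** With 32/90 positive controls, 43/90 in the vitamin A arm is the smallest count that reaches one-sided significance: p̄ = 75/180, Z = 0.1222/0.0735 = 1.66. The gap is 11 tumors (12.2 points). A 5-point shift supplies 4.5 of them, about 41%.

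**Step 4: masked reading for comparison.** Masking does not make readings accurate, but it makes the error unrelated to arm. If both arms are read at 35%, the one-sided rate is 5.1%. If both are over-read to 40%, it is 5.4%.

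**The case against.** **The plan is silent; it does not say that readers know the arm.** This stands. A reader might infer from the absence of a placebo that the pathology is read unmasked. The documents do not support that: they do not use the term open-label, do not say that allocation is sent to the laboratory, and have no arm field on Appendix F. The supportable statement is that masking is not specified.

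**Automation may protect the endpoint.** This stands in part. The sentence in Section 7.1.2 can be read as applying digital and automated methods to node density only, or to the tumor call as well. For nodes, automation comes first and manual grading is a fallback, which limits reader influence there. One might also infer that staff may override an automated result. The plan contains no such step; it allows manual node grading if needed.

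**The three pathology outcomes are not equally exposed.** This stands. The calculation concerns the tumor GC call only. Necrosis and node density are secondary, and necrosis comes from routine pathology.

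**The shifts are invented, and the largest figures depend on the test.** The documents give no reader-agreement data, so no shift can be called likely. Ten points would mean miscalling about 15% of truly negative tumors in one arm only, which is not small against an 18-point design effect. The one-sided rule appears only in the power statement, and the z test stands in for the contingency-table and logistic analyses. The rise is smaller under the other two tests but does not vanish.

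**It is a pilot.** This carries little weight: Section 11.1 powers a comparative hypothesis with 90 per arm.

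**Conclusion.** The concern holds as a gap in the stated safeguards. The trial has no placebo, its primary outcome is a present/absent call, and nothing specified keeps treatment arm from whoever makes that call or the fallback node grade.

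Under the assumed one-arm shift of 3 to 5 points, the false-positive rate would be about 11% to 18% instead of 5% (one-sided z), or 6% to 11% instead of 2.6% (upper tail of a two-sided 0.05 test). These figures rest on a true 35% in both arms, 90 read tumors per arm, and a shift confined to the vitamin A arm. They measure how sensitive the result is to biased reading. They do not show that bias will occur, and it would be wrong to conclude that the primary result is invalid or that the sample-size calculation is in error. This is an inexpensive improvement that the plan should adopt.

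**What to change.** Add to Section 7.1.2:

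- Research IHC slides and digital images from both arms carry a study code that does not show the arm.
- The same readers read them in batches that mix the two arms.
- Tumor GC presence and location, and node GC density or grade, are recorded on a coded Appendix F before the code is linked to arm.
- Image-analysis settings are fixed before linkage.

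The same edit should say whether automated methods apply to the tumor call or only to nodes.

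For necrosis, take the present/absent value from the existing pathology report with the arm concealed from the person abstracting it, and note that the report itself may not have been masked. No separate re-read is required.

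The cost is a short protocol edit, the coding step, and someone to hold the code; the registrar, who already assigns the arm under Section 4.0, is one option. Sample size, treatment and patient procedures do not change.

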8.1 Adverse Event List for Vitamin A

Check with your doctor immediately if any of the following side effects occur while taking vitamin A:

- Bleeding from gums or sore mouth
- bulging soft spot on head (in babies)
- confusion or unusual excitement
- diarrhea
- dizziness or drowsiness
- double vision
- headache (severe)
- irritability (severe)
- peeling of skin, especially on lips and palms
- vomiting (severe)

Check with your doctor as soon as possible if any of the following side effects occur while taking vitamin A:

- Bone or joint pain
- convulsions (seizures)
- drying or cracking of skin or lips
- dry mouth
- fever
- general feeling of discomfort or illness or weakness
- headache
- increased sensitivity of skin to sunlight
- increase in frequency of urination, especially at night, or in amount of urine
- irritability
- loss of appetite
- loss of hair
- stomach pain
- unusual tiredness
- vomiting
- yellow-orange patches on soles of feet, palms of hands, or skin around nose and lips

8.2 Adverse Event Characteristics

- **CTCAE term (AE description) and grade:** The descriptions and grading scales found in the revised NCI Common Terminology Criteria for Adverse Events (CTCAE) version 5.0 will be utilized for AE reporting. All appropriate treatment areas should have access to a copy of the CTCAE version 5.0. A copy of the CTCAE version 5.0 can be downloaded from the CTEP web site (<http://ctep.cancer.gov>).
- **‘Expectedness’:** AEs can be ‘Unexpected’ or ‘Expected’ (see Section 7.1 above) for expedited reporting purposes only.
- **Attribution of the AE:**
 - Definite – The AE is **clearly related** to the study treatment.
 - Probable – The AE is **likely related** to the study treatment.
 - Possible – The AE **may be related** to the study treatment.
 - Unlikely – The AE is **doubtfully related** to the study treatment.
 - Unrelated – The AE is **clearly NOT related** to the study treatment.

8.4 DSMC SAE Reporting Requirements

The Data Safety and Monitoring Committee (DSMC) is responsible for reviewing SAEs for CCCWFU Institutional studies as outlined in [Appendix C](#). DSMC currently requires that all unexpected 4 and all grade 5 SAEs on these trials be reported to them for review. All CCCWFU Clinical Research Management (CRM) staff members assisting a Principal Investigator in investigating, documenting and reporting an SAE qualifying for DSMC reporting are responsible for informing a clinical member of the DSMC as well as the entire committee via the email notification procedure of the occurrence of an SAE.

8.5 WFUHS IRB AE Reporting Requirements

Any unanticipated problems involving risks to subjects or others and adverse events shall be promptly reported to the IRB, according to institutional policy. Reporting to the IRB is required regardless of the funding source, study sponsor, or whether the event involves an investigational or marketed drug, biologic or device. Reportable events are not limited to physical injury, but include psychological, economic and social harm. Reportable events may arise as a result of drugs, biological agents, devices, procedures or other interventions, or as a result of questionnaires, surveys, observations or other interactions with research subjects.

All members of the research team are responsible for the appropriate reporting to the IRB and other applicable parties of unanticipated problems involving risk to subjects or others. The Principal Investigator, however, is ultimately responsible for ensuring the prompt reporting of unanticipated problems involving risk to subjects or others to the IRB. The Principal Investigator is also responsible for ensuring that all reported unanticipated risks to subjects and others which they receive are reviewed to determine whether the report represents a change in the risks and/or benefits to study participants, and whether any changes in the informed consent, protocol or other study-related documents are required.

Any unanticipated problems involving risks to subjects or others occurring at a site where the study has been approved by the WFUHS IRB (internal events) must be reported to the WFUHS IRB within 7 calendar days of the investigator or other members of the study team becoming aware of the event.

Any unanticipated problems involving risks to subjects or others occurring at another site conducting the same study that has been approved by the WFUHS IRB (external events) must be reported to the WFUHS IRB within 7 calendar days of the investigator or other members of the study team becoming aware of the event.

Any event, incident, experience, or outcome that alters the risk versus potential benefit of the research and as a result warrants a substantive change in the research protocol or informed consent process/document in order to insure the safety, rights or welfare of research subjects.

9.0 Pharmaceutical Information

A list of the adverse events and potential risks associated with the commercial agent administered in this study can be found in [Section 8.0](#).

9.1 Pharmaceutical Accountability

All drugs used in this protocol are commercially available.

9.2 Vitamin A

Product Description: Vitamin A is provided as retinyl palmitate in 10,000 IU capsules from Major Pharmaceuticals.

Storage:

Vitamin A stock bottles will be purchased and stored in the investigational pharmacy. Temperature conditions will be monitored per standard practice. Unopened vials of Vitamin A are stable until the expiration date indicated on the package when stored at controlled room temperature.

Route of Administration: Oral

Drug Accountability: Patients will be asked to record the time and date of medication self-administration with form attached in Appendix.

Disposal: Dispose through the Institutional waste stream and guidelines.

10.0 Data Management

Informed consent document	EPIC
Protocol registration form (Appendix A)	WISER/OnCore
Baseline Tobacco Use (Appendix D)	WISER/OnCore
Adverse Events Log (Appendix E)	WISER/OnCore
Outcomes Data Collection (Appendix F)	WISER/OnCore
Survival Form (Appendix G)	WISER/OnCore

11.0 Statistical Considerations

11.1 Power and Sample Size

Roughly 35% of lung cancers express germinal centers (GC) with the majority of GCs being detected at the tumor margin. Given our target sample size of n=90 patients per arm, we will have 80% power, using a one-tailed alpha of 0.05, to detect an increase to 53% expressing GCs in the treatment arm, given the expected “background” 35% in the standard-of-care arm. Given the current surgical volume, it is estimated that we will enroll 90 patients per year, so that total accrual will last approximately 2 years.

11.2 Method of Randomization

Patients will be randomized in a 1:1 ratio to receive the vitamin A treatment intervention or standard of care. Patients will be stratified for randomization based on pre-operative stage (stage 1, 2, or 3).

11.3 Analysis of Primary Objective

11.3.1 The outcome for our primary objective is dichotomous—GCs present/absent. Following basic bivariate analysis in contingency tables of presence/absence by treatment arm we will model presence/absence of GCs in a logistic regression model as a function of treatment arm, stage, and age at diagnosis. We will first examine the statistical interaction term between stage and treatment arm, and if it is significant, we will present findings stratified by stage. If it is not significant, we will remove the interaction term from the final model and include stage as a simple covariate only.

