2.0 Objectives

2.1 Primary Objective

- 2.1.1 To compare the percentage of resected cancers containing germinal centers (GCs) in patients who receive neoadjuvant vitamin A to controls.

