11.4 Analysis of secondary objectives

11.4.1 Number of GCs per unit area in lymph nodes will be quantified ordinally only, in mutually exclusive ordered groups of high, moderate, low, or absent. We will examine association between treatment arm and rank order of number of GCs in contingency table analysis using methods that incorporate the ordinal ranking of one of the variables. We will also model the outcome of rank order of number of GCs as a function of treatment arm, age, and stage using ordinal logistic regression. As above we will first examine whether there is a significant

interaction between stage and treatment arm with respect to the outcome, and if so will present findings stratified by stage.

11.4.2 Presence/absence of necrosis will be analyzed in a similar manner as the dichotomous outcome of presence/absence of GCs, described above under 11.3.1.

11.4.3 Overall survival will be estimated in treatment and control groups using standard Kaplan-Meier life table analyses and will also be evaluated in the multivariable setting using Cox proportional hazards modeling, where covariates of age and stage will be included. As described above we will first examine whether the statistical interaction between stage and treatment arm is significant.

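### An interaction pre-test with no stated level chooses the final primary model, no primary test is named, and an overall stage-adjusted effect is not guaranteed

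*Combined protocol and SAP*

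**What the plan says.** The primary objective in Section 2.1 is a single comparison: "To compare the percentage of resected cancers containing germinal centers (GCs) in patients who receive neoadjuvant vitamin A to controls". Section 11.1 sizes the trial for that comparison, with 90 patients per arm and 80% power, "using a one-tailed alpha of 0.05, to detect an increase to 53% expressing GCs in the treatment arm", against 35% in controls. Section 11.2 stratifies the randomisation by pre-operative stage in three levels.

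Section 11.3.1 then lays out three steps for the primary outcome:

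- An unadjusted look at the data: "Following basic bivariate analysis in contingency tables of presence/absence by treatment arm". No test is named for it.
- A logistic model on arm, stage and age at diagnosis, in which the stage-by-arm interaction is examined first.
- A fork. On the interaction, "if it is significant, we will present findings stratified by stage". Otherwise, "If it is not significant, we will remove the interaction term from the final model and include stage as a simple covariate only".

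The section gives no level for the interaction test and no level or sidedness for the treatment comparison. It also does not say whether the table or the model decides the primary objective.

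Section 11.4 repeats the interaction-first step for the secondary outcomes. For lymph-node germinal centers it looks for a significant "interaction between stage and treatment arm with respect to the outcome, and if so will present findings stratified by stage". Necrosis follows the primary analysis. Survival also begins with the interaction. Overall comparisons that do not depend on the interaction are planned alongside: "We will examine association between treatment arm and rank order of number of GCs in contingency table analysis" in 11.4.1, and Kaplan-Meier estimates by arm in 11.4.3.

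**The concern.** The trial asks one overall question and is sized for one overall test, but the data decide what the final model reports. If the interaction is significant, the reader is promised stage-specific results and no single adjusted treatment effect. Nothing explains how three stage results relate to the one-tailed 0.05 in Section 11.1. Because the pre-test has no level, the point at which the plan switches branches is also undefined and could be settled after the results are seen.

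Two things are at stake. If a positive result in any one stage could be claimed as success, the error rate exceeds the planned 5%. If the stage results are only descriptive, some trials with a real and uniform benefit end without the overall adjusted claim. Individual stages are too small to carry the conclusion in its place. For the secondary outcomes, only the overall adjusted effects are left conditional in this way.

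**Working it through.** **1. The plan's own figure.** Inputs from Section 11.1: n = 90 per arm, 35% vs 53%, one-sided 0.05 (z = 1.645). The mean proportion is 0.44.

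Power = Φ{[0.18 − 1.645·√(2·0.44·0.56/n)] / √[(0.35·0.65 + 0.53·0.47)/n]}

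With n = 90 this is Φ[(0.18 − 1.645·0.0740)/0.0728] = Φ(0.80) = 78.8%. With unpooled variance throughout it is 79.6%. The stated 80% is therefore reproduced to within about a point, as the power of one overall two-proportion test with no pre-test.

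**2. Power within a stage.** The documents give no stage mix, so two are assumed per arm: 54/22/14 and 30/30/30. The same formula gives:

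| Patients per arm in the stage | Power, one-sided 0.05 |
|---|---|
| 54 | 59.6% |
| 30 | 40.3% |
| 22 | 32.6% |
| 14 | 24.3% |

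**3. Simulation of the two-step rule.** There were 100,000 trials per scenario with 90 per arm. The logistic model had arm and stage (age omitted), a 2-df likelihood-ratio interaction test, one-sided Wald tests, and a pooled z test for the overall table. Assumed: pre-test at 0.05 unless stated, and the same control rate in every stage. Monte Carlo standard error is about √(0.05·0.95/100,000) = 0.07 points for error rates and √(0.8·0.2/100,000) = 0.13 points for power.

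| | Mix 54/22/14 | Mix 30/30/30 |
|---|---|---|
| **No effect (35% in both arms)** | | |
| Table by arm | 4.97% | 5.03% |
| Fixed adjusted model | 5.00% | 5.06% |
| Interaction significant | 5.90% | 5.58% |
| Two-step, any significant stage counts | 7.97% | 8.12% |
| Two-step, Bonferroni across stages | 6.49% | 6.62% |
| Two-step, stage results descriptive | 4.70% | 4.78% |
| **Uniform effect (35% vs 53%)** | | |
| Table by arm | 79.50% | 79.67% |
| Fixed adjusted model | 80.12% | 80.26% |
| Interaction significant | 5.68% | 5.48% |
| Interaction and adjusted effect both significant | 4.57% | 4.35% |
| Two-step, stage results descriptive | 75.55% | 75.91% |

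*Excess error.* Without an effect, the unstratified branch contributes 4.70% (4.78%). The stratified branch adds 7.97 − 4.70 = 3.27 points (8.12 − 4.78 = 3.34). A triggered pre-test therefore comes with at least one stage significantly favouring vitamin A in 3.27/5.90 = 55% (3.34/5.58 = 60%) of cases.

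*Power loss.* It equals the trials in which the pre-test triggers although the overall adjusted effect is significant: 80.12 − 4.57 = 75.55% and 80.26 − 4.35 = 75.91%. In 3.5 to 3.6% of all trials with this uniform effect, the pre-test triggers and at least one stage points towards control.

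**4. Range over the unstated pre-test level.** From 0.01 to 0.10, any-stage error runs from 5.7% to 9.9%, and power under the descriptive reading from 79.4% down to 71.2%.

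**5. Sensitivity of the 8%.** All at pre-test level 0.05:

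- Homogeneity test of the stage log odds ratios, Cochran-Mantel-Haenszel overall test, mixes 33/33/33, 60/25/15 and 70/20/10%: 6.7 to 7.5%.
- Logistic model with age included, 3,000 trials, mix 60/25/15%: 8.6%.
- Control rates of 40/30/20% by stage, mix 54/22/14: 7.4%.

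**The case against.** The strongest reply is that an overall comparison is planned whatever the interaction shows. The table by arm comes before the model, answers the objective in Section 2.1 directly, and matches the unadjusted calculation in Section 11.1. On that reading there is no cost. This stands as a possible reading, but the plan does not state it. Section 11.3.1 presents the table as a preliminary and reserves the idea of a final model for the logistic regression, which points the other way.

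Second, the text speaks of presenting stratified findings, which is the language of reporting and not of decision. The plan contains no rule that any significant stage counts as success. That is correct, so the 8% applies only if that rule is adopted. Read descriptively, error is not inflated, and the cost is power.

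Third, little information is lost. When the pre-test triggers under the uniform effect, the table is still significant in about 80% of those trials, and the table and the adjusted test disagree in only 0.7% of trials. This is true, but it helps only if the table is allowed to decide.

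Fourth, the figures rest on assumptions. Section 1.0 links germinal centers to a lower risk of nodal metastasis, so a common 35% across stages is doubtful. This stands, and the any-stage error is better given as roughly 7 to 9%. The direction does not change.

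Finally, Appendix B titles the trial a pilot, and the endpoint is a tissue marker. That limits the consequences. It is nevertheless a randomised trial of 180 patients with a stated alpha and power, and those hold only for one fixed overall test.

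**Conclusion.** The concern holds. A pre-test without a level determines whether the final primary model yields one overall adjusted effect or only stage-specific findings, and no analysis is named as decisive. The cost is moderate and depends on the reading: none if the table is primary; one-sided error of roughly 7 to 9% if the model is primary and any stage can succeed; and power of about 76% instead of 80% if the stratified results are descriptive.

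The last two figures assume a pre-test at 0.05 and stage mixes and stage-specific control rates that the documents do not give. The defect in the text does not depend on those assumptions. Nor does the stated 80% need correcting: it is right for a single overall comparison, which is what the plan should commit to. With 24 to 60% power per stage under the assumed mixes, stratified findings cannot replace it.

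**What to change.** In Section 11.3.1, name one overall primary test at one-sided 0.05 and state that it is reported whatever the interaction shows. The suggested choice is the treatment coefficient from the logistic model with pre-operative stage (the randomisation stratum) and age, without the interaction term, with the table by arm as supportive. Naming the table as primary would also remove the problem. Report the interaction test, with its level stated, and the stage-specific estimates with confidence intervals as exploratory.

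In Sections 11.4.1 to 11.4.3, state that the overall adjusted effect is always reported, next to the ordinal table and the Kaplan-Meier estimates already planned.

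The cost is wording in Section 11, with no added patients or data. The one real concession is that stage-specific findings can no longer be confirmatory. With the same 90 per arm, the fixed adjusted test has simulated error of 5.0 to 5.1% and power of 80.1 to 80.3%; the table has 5.0% and 79.5 to 79.7%.
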